7.3. Unscheduled Visits

If, during the investigation, a subject requires an unscheduled visit to the clinical site, the following information will be collected at a minimum:

- Chief complaint prompting the visit. If the reason is an adverse event, the applicable eCRF for the adverse event must be completed and subject record completed as appropriate
- Date and time of the visit and all procedures completed at the unscheduled visit
- Review of adverse event and concomitant medications
- Documentation of any test article dispensed or collected from the subject, if applicable
- Slit lamp findings (using the Slit Lamp Classification Scale)

If the Investigator withdraws a subject from the study, the final study visit case report forms must be completed indicating the reason(s) why the subject was withdrawn. The subject record must be completed documenting the date and primary reason for withdrawal and the study CRA notified.

Any ocular and non-ocular Adverse Events that are ongoing at the time of the study visit will be followed by the Investigator, within licensure, until they have resolved, returned to pre-treatment status, stabilized, or been satisfactorily explained. If further treatment i.e., beyond licensure is required, the subject will be referred to the appropriate health care provider.

The following information will be collected during an unscheduled visit.

Unscheduled Visit		
Step	Procedure	Details
U.1	Chief Complaints	Record the subject's chief complaints for reasons for the unscheduled visit
U.2	Adverse Events and Concomitant Medications Review	Review the subject's concomitant medications and record any changes from the previous study visit.
U.3	Subject Reported Ocular Symptoms	Subjects will respond to a verbal open-ended symptoms questionnaire.
U.4	Entrance VA	Record the entrance distance and near visual acuity (OD, OS and OU) to the nearest letter. For near measures use the ETDRS 2000 Series Chart 1 or 2. The acuity will be recorded to the nearest letter OD, OS and OU.
U.5	Subjective Sphero-cylindrical Refraction	An optimal, binocular balanced distance sphero-cylindrical refraction will be performed. Record the refraction and distance visual acuity to the nearest letter.
U.6	Biomicroscopy	FDA Slit Lamp Classification Scale will be used to grade the findings and determine eligibility.

Unscheduled Visit			
		
For the conjunctival redness [REDACTED] 0.5 unit increments will be used in the grading.
 
Corneal Staining Assessment [REDACTED] will be graded in 1.0 increments.
 
If the clearance of the fluorescein needs to be expedited, preservative-free rewetting drops may be instilled.
	
U.7	Lens Dispensing	Additional study lenses may be dispensed when required.	[REDACTED]
U.8	Lens Fit Assessment:	
Evaluate and grade lens centration, primary gaze movement, upgaze movement and tightness (push-up test).
 
The subject should not proceed to wear the lenses if any of the following is observed:
 
 presence of limbal exposure (appearance of clear cornea) in any gaze presence of edge lift presence of unacceptable movement (excessive or insufficient) in all three movement categories (primary gaze, upgaze, and push-up). 
If either lens is deemed unacceptable, the subject will be discontinued from the study. Remove the lenses, perform a slit-lamp evaluation, and complete the Final Evaluation form.
	[REDACTED]
U.9	Exit Visual Acuity	
Record the subject's exit distance and near visual acuity (OD, OS and OU) to the nearest letter.
 
For near measures use the ETDRS 2000 Series Chart 1 or 2. The acuity will be recorded to the nearest letter OD, OS and OU.
	[REDACTED]

7.4. Laboratory Procedures

Not Applicable

8. SUBJECTS COMPLETION/WITHDRAWAL

8.1. Completion Criteria

Subjects are considered to have completed the study if they:

- provided informed consent
- they are eligible
- completed all study visits

8.2. Withdrawal/Discontinuation from the Study

A subject will be withdrawn from the study for any of the following reasons:

- Subject death during the study period
- Subject withdrawal of consent
- Subject not compliant to protocol
- Subject lost to follow-up
- Subject no longer meets eligibility criteria (e.g. the subject becomes pregnant)
- Subject develops significant or serious adverse events causing discontinuation of study lens wear
- Subjects who have experienced a Corneal Infiltrative Event (CIE)
- Investigator's clinical judgment regarding the subject safety reasons (that it is in the best interest of the subject to stop treatment)
- Subject missed two consecutive study visits
- Subject not compliant with study lens wear schedule
- Subject not successfully dispensed due to lack of efficacy and safety including poor vision, poor comfort or unacceptable fit

For discontinued subjects, the Investigator will:

- Complete the current visit (scheduled or unscheduled)
- Complete the Final Evaluation, indicating the reason that the subject was discontinued from the study
- Record the spherocylindrical refraction with best corrected distance visual acuity
- Collect used test article(s) (worn or brought to the visit) from the subject and discard them, unless otherwise stated in Section 6.7
- Collect all unused test article(s) from the subject

An additional subject may be enrolled if a subject discontinues from the study prematurely.

In cases where a subject is lost to follow-up, every possible effort must be made to contact the subject and determine the reason for discontinuation/withdrawal. The measures taken to follow up must be documented including two written attempts and a certified letter (or equivalent) as the final attempt.

9. PRE-STUDY AND CONCOMITANT INTERVENTION/MEDICATION

Concomitant medications will be documented during screening and updated during the study. Disallowed medications and therapies are medications or therapies that contraindicate contact lens wear. See the Exclusion criteria for specific details.

10. DEVIATIONS FROM THE PROTOCOL

Investigator will notify study sponsor upon identification of a protocol deviation. Major protocol deviations must be reported to the sponsor within 24 hours after discovery of the protocol deviation. The Investigator will report deviations per IRB/IEC requirements. All deviations will be tracked, and corrective actions implemented as appropriate.

If it becomes necessary for the Investigator to implement a deviation in order to eliminate an immediate hazard to the trial subject, the Investigator may implement the deviation immediately without notification to the sponsor. Within 24 hours after the implemented deviation, the Investigator must notify and provide the rationale to the Sponsor and, as required, the IEC/IRB.

11. STUDY TERMINATION

If more than 2 subjects in the investigational soft contact lens group develop serious expected (e.g., definite or probable MK) or unexpected device related adverse events, the study will be suspended. Upon review and consultation with IRB, DMC, and JJV safety review committee, the study may be terminated. This potential stopping rule is established based on our trial involving approximately 200 subjects wearing the investigational soft contact lens for up to 3 years with an assumed MK rate that is below 0.2% per patient-year. The rate of 0.2% per patient year is the established rate for extended wear lenses in adults, which was requested by the FDA as a criterion for evaluating a contact lens for pediatric use in an FDA response to a pre-IDE submission. To be conservative, 200 independent patient years were used in the calculation. The probability of observing 2 cases or more incidents of MK is 0.061, and 3 cases or more incidents of MK is 0.007 (given a MK rate of 0.2% per patient year).

The occurrence of one or more Unanticipated Serious Adverse Device Effect (USADE), or any SAE where the relationship to study agent cannot be ruled out, may result in stopping further dispensing of test article. In the event of a USADE or SAE, the Sponsor may unmask the treatment regimen for the subject(s) and will discuss this with the Investigator before any further subjects are enrolled.

The Sponsor will determine when a study will be stopped. The Principal Investigator always has the discretion to initiate stopping the study based on patient safety or if information indicates the study's results are compromised.

JJVC reserves the right to terminate the study at any time for any reason. Additionally, the IEC/IRB reserves the right to terminate the study if an unreasonable risk is determined. The study can be terminated by the Principal Investigator at the individual clinical site due to

specific clinical observations, if in their opinion, after a discussion with JJVC, it is determined that it would be unwise to continue at the clinical site.

JJVC (and the IEC/IRB and DMC, if applicable) will evaluate all adverse events. If it is determined that an adverse event presents an unreasonable risk, the investigation, or that part of the investigation presenting the risk, will be terminated, as soon as possible.

Should the study be terminated (either prematurely or as scheduled), the Investigator will notify the IEC/IRB and Regulatory Authority as required by local regulatory requirements.

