1.4. Summary of Known Risks and Benefits to Human Subjects

Anticipated risks and adverse reactions with this lens are similar to those with other soft daily wear contact lenses used to correct presbyopia. A listing of examples of adverse reactions is found in the Section 13 of this protocol. The investigator should follow normal clinical guidelines regarding examination and care of subjects who participate in this trial. Refer to study lens package insert for additional details. The study multifocal contact lens is designed for the correction of refractive spherical ametropia and presbyopia. one study contact lenses is manufactured in lotrafilcon B and will be worn in a daily wear, reusable modality. The other study contact lens is manufactured in deleficon A and will be worn in a daily wear, disposable modality. These lens is not intended for extended wear in this study.

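### The Synopsis and Section 11 disagree on whether one serious event must halt dispensing, and the stated basis of the more-than-2 suspension threshold does not match this trial

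*Combined protocol and SAP*

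**What the plan says.** **One-event rule.** The Synopsis (Study Termination row) and Section 11 (second paragraph) both address a single unanticipated device effect, or any SAE for which a link with the study product cannot be excluded. The Synopsis makes a halt to dispensing mandatory (*will*). Section 11 makes it discretionary (*may*). On the linked step, the Synopsis says that the medical monitor *may* discuss unmasking with the investigator before more subjects enter; Section 11 says that the sponsor *will*.

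**More-than-2 rule.** Section 11 (first paragraph) begins "If more than 2 subjects in the investigational soft contact lens group develop serious expected" and, after an MK example, continues "or unexpected device related adverse events, the study will be suspended". The rule is said to be "established based on our trial involving approximately 200 subjects wearing the investigational soft contact lens for up to 3 years". The MK rate is described in these words: "The rate of 0.2% per patient year is the established rate for extended wear lenses in adults". Its origin as a criterion is given separately: "which was requested by the FDA as a criterion for evaluating a contact lens for pediatric use". On exposure: "To be conservative, 200 independent patient years were used in the calculation". The result: "The probability of observing 2 cases or more incidents of MK is 0.061, and 3 cases or more incidents of MK is 0.007".

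**This trial.** About 50 subjects are to be enrolled and 40 to complete, over 2–4 months (Section 4.3). Ages are 40 to 70 (Section 3.2, criterion 3). Each lens type is worn for about 8–12 days (Sections 1.2 and 4.2). Wear is daily: "These lens is not intended for extended wear in this study" (Section 1.4). Every subject is assigned both lenses, in one of two orders (Section 5.1).

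**The concern.** These paragraphs tell the ethics committee and the investigators what happens after a serious event. On the first such event they give two different instructions. MK is a listed ocular SAE (Section 13.1), so one possibly related case meets both one-event triggers. Under the Synopsis, dispensing stops. Under Section 11, it may continue, and suspension becomes compulsory only at the third affected subject. Lenses are dispensed at Visits 1, 2, 4 and 5, so the choice can affect subjects already in the study as well as new ones.

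The threshold of more than 2 is then supported by probabilities that rest on a size, duration, wear modality and rate criterion that this protocol does not have. A reader would take 0.007 as the chance of a false suspension here. It is not.

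**Working it through.** **1. The one-event rule, side by side**

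| | Synopsis | Section 11 |
|---|---|---|
| Device-effect trigger | one or more UADE | one or more USADE |
| SAE trigger | any SAE with relationship not excluded | the same |
| Dispensing | *will* stop | *may* stop |
| Discussion with investigator | *may* | *will* |

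The SAE row is the same in both places, so the conflict in the third row stands whatever the two device-effect labels mean. The labels do not remove it either: Section 13.1 defines UADE entirely by serious effects, and Section 13.4.1 puts the word serious in brackets inside the same term. I found no statement that one section takes precedence over the other.

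**2. The printed probabilities**

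Inputs from Section 11: n = 200 patient-years, p = 0.002 per patient-year. With X ~ Binomial(200, 0.002):

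- P(X = 0) = 0.998²⁰⁰ = 0.6700
- P(X = 1) = 200 × 0.002 × 0.998¹⁹⁹ = 0.2686
- P(X = 2) = 19,900 × 0.002² × 0.998¹⁹⁸ = 0.0536
- P(X ≥ 2) = 0.0614 (printed 0.061)
- P(X ≥ 3) = 0.0078 (printed 0.007, which is truncated; it rounds to 0.008)

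The Poisson version (mean 0.4) gives 0.0616 and 0.0079. Using 200 × 3 = 600 patient-years would give 0.337 and 0.120. So the printed figures come from 200 patient-years, as the text says.

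**3. The same calculation for this trial**

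Inputs: 50 enrolled (Section 4.3) and 8–12 days per lens (Section 1.2; this agrees with 3 ± 1 plus 7 ± 1 days). Patient-years = subjects × days / 365.25. Mean MK count λ = patient-years × 0.002. For small λ, the Poisson P(X ≥ 3) is close to λ³/6.

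| Exposure counted | Patient-years | 200 ÷ patient-years | λ | P(X ≥ 3) |
|---|---|---|---|---|
| One lens, 8 days | 50 × 8 / 365.25 = 1.095 | 183 | 0.0022 | 1.7 × 10⁻⁹ |
| One lens, 12 days | 50 × 12 / 365.25 = 1.643 | 122 | 0.0033 | 5.9 × 10⁻⁹ |
| Both lenses, 16 days | 50 × 16 / 365.25 = 2.190 | 91 | 0.0044 | 1.4 × 10⁻⁸ |
| Both lenses, 24 days | 50 × 24 / 365.25 = 3.285 | 61 | 0.0066 | 4.7 × 10⁻⁸ |

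With 40 completers, exposure is 0.88–1.31 patient-years on one lens and 1.75–2.63 on both. Section 11's own inputs give 200 × 0.002 = 0.4 expected MK cases, against 0.002–0.007 here.

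**4. Scope**

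The probabilities concern MK alone. The rule counts any serious expected or unexpected device-related event. The documents give no rate for these events together, so the behaviour of the full rule cannot be calculated from them.

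**The case against.** The strongest reply on the threshold is that it works the same way whether or not a derivation is printed. Section 11 discloses its inputs and conditions its figures on the 0.2% rate. The error also runs in one direction: the printed figure overstates how often MK alone would suspend this trial. If the Synopsis wording governs, one possibly related SAE already halts dispensing and the more-than-2 rule is largely a backstop. All of this stands, and it makes the one-event conflict the more consequential part.

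Other safeguards also limit the effect. The sponsor, the investigator and the ethics committee can each stop the study (Section 11). Subjects whose serious or significant events end lens wear are withdrawn (Section 8.2). Such events are reported within 24 hours (Section 13.4.1). These do not settle which one-event instruction applies.

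Four stronger readings are tempting and are not supported:

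- *The text was copied from another trial.* The mismatches make this a strong inference, but Section 11 says only that the trial is the sponsor's own.
- *The threshold is wrong or unsafe.* Nothing here shows that. The MK calculation does not measure the all-event rule.
- *The arithmetic is wrong.* It reproduces, apart from one truncated digit.
- *The rule plainly counts events on either lens.* The documents are mixed. The Synopsis and Section 1.1 call both products test lenses, while Sections 2.3, 5.1 and 6.1 separate Test from Control. The group named in the rule is undefined.

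A reader might also argue that UADE and USADE differ, since the abbreviation list has both. The shared SAE trigger makes that immaterial.

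**Conclusion.** The point holds in two parts. First, the Synopsis and Section 11 contradict each other on whether dispensing must stop after one possibly related SAE. This rests on the text alone. Second, the stated basis of the more-than-2 threshold does not match this protocol: 200 patient-years is 61 to 183 times the planned exposure, and at the same rate the chance of 3 or more MK cases is at most about 5 × 10⁻⁸, not 0.007.

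The second part assumes 50 enrolled, full wear within the stated range, a Poisson count, and Section 11's own 0.2% rate, which is an extended-wear rate applied here to daily wear only for comparison. A few more or fewer subjects would not change the conclusion. No endpoint or analysis is affected. The point should be fixed because it concerns what is done after a serious event and the correction is cheap.

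**What to change.** - Reconcile the Synopsis and Section 11 so that one wording governs the one-event trigger, with one label for the device effect, and align the linked step on discussion with the investigator. The sponsor decides which wording stands.
- In Section 11, remove the probabilities based on 200 subjects and 3 years, or state that they do not apply to this trial. In either case, restate the basis of the threshold for this protocol's own size, exposure and wear modality. Deletion alone would leave the threshold with no stated basis.
- State which lens or lenses the investigational group in the rule covers, given that every subject is assigned both.

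No threshold or stopping rule is proposed here. The cost is wording in two places and, if made by amendment, submission to the IEC/IRB for review and approval where appropriate (Section 18.3). Visits, data collection and analysis do not change. Settling the one-event wording would affect conduct only if such an event occurs.

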12. PROCEDURE FOR HANDLING PRODUCT QUALITY COMPLAINTS

A Product Quality Complaint (PQC) refers to any written, electronic, or oral communication that alleges deficiencies related to the identity, quality, durability, reliability, safety, effectiveness or performance of test articles after they have been released for clinical trial use.

Potential complaints may come from a variety of sources including but not limited to subjects, clinical research associates (CRA), clinical operations managers (COM), medical monitors, and site personnel, etc. The following are not considered product quality complaints:

- Subject satisfaction inquiries reported via “Subjective Questionnaires” and “Patient Reported Outcomes (PRO)”
- Clinical test articles that are stored improperly or damaged after receipt at the investigational site
- Lens replacements that occur due to drops/fall-outs
- Damage deemed by clinicians or clinical staff to be caused by handling by the user, and not indicative of a quality deficiency (i.e. tears, rips, etc.), only in situations where there is no deficiency alleged by the subject

Within 24 hours of site personnel becoming aware that a PQC has occurred, the PQC must be recorded in the EDC system, which will trigger an automatic email notification to the appropriate COM/CRA and Clinical QA representative. In cases where the EDC system in use is not configured to send automatic notifications or when an EDC system is not used, the COM/CRA is responsible for notifying Clinical QA upon discovery that a PQC has occurred.

Upon receipt of the EDC notification, the COM/CRA will contact the study site to collect additional information which will include:

- Date the complaint was received/recorded in the EDC System (Date of Sponsor Awareness)
- Who received the complaint
- Study number
- Clinical site information (contact name, site ID, telephone number)
- Lot number(s)
- Unique Subject Identifier(s)
- Indication of who first observed complaint (site personnel or subject)

- OD/OS indication, along with whether the lens was inserted
- Any related AE number if applicable
- Detailed complaint description (scheduled/unscheduled visit, wear time, symptoms, resolution of symptoms, etc.)
- Eye Care Provider objective (slit lamp) findings if applicable
- Confirmation of product availability for return (and tracking information, if available), or rationale if product is not available for return

[REDACTED]

Once a complaint is received, it will be assessed by the COM, CRA, or trained site personnel to determine if it is an Adverse Event/Serious Adverse Event (AE/SAE). If the complaint results in an AE/SAE, the COM/CRA, or trained site personnel will follow Section 13 of this protocol. If the AE/SAE was potentially the result of a product quality related deficiency, these procedures also applies and will be executed in parallel.

In some cases, a PQC form may be generated in EDC by the site in error. In this event, the PQC forms will be marked “Intentionally Left Blank” or “ILB”. Justification for ILB must be documented.

13. ADVERSE EVENTS

13.1. Definitions and Classifications

Adverse Event (AE) – An AE is “any untoward medical occurrence, unintended disease or injury, or untoward clinical signs (including abnormal laboratory findings) in subjects, users or other persons, whether or not related to the investigational medical device.

NOTES:

Note 1 to entry: This definition includes events related to the investigational medical device or the comparator.

Note 2 to entry: This definition includes events related to the procedures involved.

Note 3 to entry: For users or other persons, this definition is restricted to events related to investigational medical devices.”¹

An AE includes any condition (including a pre-existing condition) that:

1. Was not present prior to the study, but appeared or reappeared following initiation of the study
2. Was present prior to the study but worsened during the study. This would include any condition resulting from concomitant illnesses, reactions to concomitant medications, or progression of disease states
3. Pregnancy must be documented as an adverse event and must be reported to the clinical monitor and to the Sponsor immediately upon learning of the event

Serious Adverse Event (SAE) – An SAE is any untoward medical occurrence that:

- Results in death
- Is life threatening
- Requires in-patient hospitalization or prolongation of existing hospitalization

- Results in persistent or significant disability/incapacity (e.g., a sight threatening event, a significant persistent or permanent change, impairment, damage, or disruption to the subject's body)
- Is a congenital anomaly/birth defect, or
- Requires intervention to prevent permanent damage (the use of the test article resulting in a condition which requires medical or surgical intervention to preclude permanent impairment of the body structure or a body function). Important medical events that may not result in death, be life-threatening, or require hospitalization may be considered an SAE when, based upon appropriate medical judgment, they may jeopardize the patient or subject and may require medical or surgical intervention to prevent one of the outcomes listed in the above definition

Diagnoses and conditions that are considered Ocular Serious Adverse Events include, but not limited to:

- Microbial Keratitis (MK)
- Iritis (including cells in the anterior chamber)
- Permanent decrease in best spectacle corrected visual acuity equivalent to 2 acuity lines or greater
- Central Corneal Opacity
- Central Corneal Neovascularization
- Uveitis
- Endophthalmitis
- Hypopyon
- Hyphemia
- Penetration of Bowman's Membrane
- Persistent Epithelial Defect
- Limbal cell Damage leading to Conjunctivalization

Significant Adverse Events – Those events that are usually symptomatic and warrant discontinuation (temporary or permanent) of the test article (excluding Serious Adverse Events).

Diagnoses and conditions that are considered Ocular Significant Adverse Events include, but not limited to the following:

- Contact Lens Induced Peripheral Ulcer (CLPU)
- Significant Infiltrative Events (SIE)
- Superior Epithelial Arcuate Lesions (SEALS)
- Any Temporary Loss of > 2 Lines of BSCVA
- Other grade 3 or higher corneal findings, such as abrasions or edema
- Non-contact lens related corneal events - e.g. Epidemic Keratoconjunctivitis (EKC)
- Asymptomatic Corneal Scar
- Any corneal event which necessitates temporary lens discontinuation > 2 weeks

Non-Significant Adverse Events – Those conditions that are usually asymptomatic and usually do not warrant discontinuation (temporary or permanent) of the test article. However, the Investigator may choose to treat as a precautionary measure.

Diagnoses and conditions that are considered Ocular Non-Significant Adverse Events include, but not limited to the following:

- Non-significant Infiltrative Event (NSIE)
- Contact Lens Papillary Conjunctivitis (CLPC)
- Superficial Punctate Keratitis (SPK)
- Conjunctivitis: Bacterial, Viral, Allergic
- Blepharitis
- Meibomianitis
- Contact Dermatitis
- Localized Allergic Reactions
- Any corneal event not explicitly defined as serious or significant adverse event, which necessitates temporary lens discontinuation < 2 weeks

Adverse Device Effect (ADE) – An ADE is an “adverse event related to the use of an investigational medical device.

NOTES:

Note 1 to entry: This definition includes adverse events resulting from insufficient or inadequate instructions for use, deployment, implantation, installation, or operation, or any malfunction of the investigational medical device.

Note 2 to entry: This definition includes any event resulting from use error or from intentional misuse of the investigational medical device.”¹

Unanticipated Adverse Device Effect (UADE) – Any serious adverse effect on health or safety or any life-threatening problem or death caused by, or associated with, the test article, if that effect, problem, or death was not previously identified in nature, severity, or degree of incidence in the investigational plan, Investigator's Brochure or protocol, or any other unanticipated serious problem associated with the test article that relates to the rights, safety and welfare of subjects.

